Design: To address the impact of a popular, over-the-counter gel lubricant use in MSM on PrEP, investigators at Emory University will collaborate with the Centers for Disease Control and Prevention (CDC) to conduct a randomized clinical trial of 90 MSM. Men will be randomized into a 3-arm study as follows: (1) daily oral Truvada® only, (2) daily gel lubricant applied rectally only or (3) oral Truvada® plus rectal gel lubricant application daily. This study will entail 4 study visits at the Emory University Hope Clinic. During the first visit (time 0), all men will be screened for eligibility and undergo written informed consent, physical examination, rapid HIV testing, phlebotomy for screening laboratories, and randomization. During study visit 2 prior to the initiation of study product (time 1-6 weeks), participants will undergo phlebotomy, collection of rectal secretions, and rectal biopsy via rigid sigmoidoscopy for establishment of baseline values. During study visit 3 (time 4-16 weeks), men will be dispensed and instructed on the at-home application of rectal lubricant and/or oral Truvada. During study visit 4 (time 5-26 weeks), men will return after 7 consecutive days of study product use for repeat phlebotomy, collection of rectal secretions, and rectal biopsy via rigid sigmoidoscopy. After collection, biologic specimens will be immediately transported by courier to CDC (laboratory of [name]) for processing. Specimens will be processed immediately for *ex vivo* laboratory assays that will include PrEP drug concentrations, inflammatory cytokine levels, HIV target cell measurement and characterization by flow cytometry, and *in vitro* HIV infection assays. Comparison of assay results among the 3 study arms should determine if rectal lubricant usage reduces PrEP drug concentrations, increases inflammation, or increases the proportion or susceptibility of HIV target cells in the rectal mucosa.

Duration: The duration of this study is 2 years. Participants will be considered 'on-study' for no more than 26 weeks.

Sample size: For this protocol we will recruit 90 HIV-negative MSM who meet eligibility criteria outlined in the protocol.

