For this protocol, we will recruit HIV-negative MSM aged 18-49 who are willing to adhere to study procedures. There will be 4 study visits conducted over a maximum 6-month period. The first visit will be a screening visit where eligibility is determined, written informed consent is obtained, screening tests are performed, and men will be randomized to one of three study groups: 1. Use of rectal over the counter gel lubricant alone; 2. Use of oral Truvada alone; or 3. Use of rectal gel lubricant and oral Truvada. The second study visit will occur 1-6 weeks after the screening visit. During the second study visit, men will undergo a blood draw and rigid sigmoidoscopy for collection of baseline rectal secretions and biopsies. The third study visit will occur at least 3 weeks after the second study visit (4-16 weeks after the screening visit). During the 3rd study visit, men will be given lubricant and/or Truvada and instructed on their use for 7 consecutive days before study visit 4. Study visit 4 will occur at least 4 weeks after study visit 2 (5-26 weeks after the screening visit). During study visit 4, men will again undergo a blood draw and undergo a rigid sigmoidoscopy for collection of rectal secretions and biopsy samples post use of product(s) for 7 days just prior to visit. All specimens will be transported directly to the laboratory of [name] at CDC where multiple immune assays are planned to determine if the use of lubricant may affect how well PrEP works.

TITLE OF PROJECT: PrEP, LUBE, AND THE RECTAL MUCOSA IN MSM AT RISK OF HIV

Emory IRB00077593

PRINCIPAL INVESTIGATOR: [name], MPH

PROJECT DESCRIPTION

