- 2) Male to female transgender women who are not currently taking hormonal therapy or plan to take hormonal therapy for the duration of the study
- 3) Not currently taking PrEP and no plans to initiate during study
- 4) Able to provide informed consent in English
- 5) No plans for relocation in the next 6 months
- 6) Willing to undergo peripheral blood and rectal biopsy sampling
- 7) Willing to use study products as directed
- 8) Willing to abstain from receptive anal intercourse 3 days prior to study visit 2 and 10 days prior to study visit 4.
- 9) Willing to abstain from receptive anal intercourse for 1 week after study visits 2 and 4.

EXCLUSION CRITERIA

- 1) History of inflammatory bowel disease or other inflammatory, infiltrative, infectious or vascular condition involving the lower gastrointestinal tract that, in the judgment of the

investigators, may be worsened by study procedures or may significantly distort the anatomy of the distal large bowel

- 2) Significant laboratory abnormalities at baseline visit for rectal biopsies, including but not limited to:
 - a) Hgb \leq 10 g/dL
 - b) PTT $>$ 1.5x ULN or INR $>$ 1.5x ULN
 - c) Platelet count $<$ 100,000
- 3) Any known medical condition that, in the judgment of the investigators, increases the risk of local or systemic complications of endoscopic procedures or pelvic examination, including but not limited to:
 - a) Uncontrolled or severe cardiac arrhythmia
 - b) Recent major abdominal, cardiothoracic, or neurological surgery
 - c) History of uncontrolled bleeding diathesis
 - d) History of colonic, rectal, or vaginal perforation, fistula, or malignancy
 - e) History or evidence on clinical examination of ulcerative, suppurative, or proliferative lesions of the anorectal or vaginal mucosa, or untreated sexually transmitted disease with mucosal involvement
- 4) Continued need for, or use during the 14 days prior to enrollment, of the following medications:
 - a) Aspirin or more than 4 doses of NSAIDs
 - b) Warfarin, heparin (low-molecular weight or unfractionated), platelet aggregation inhibitors, or fibrinolytic agents
 - c) Any form of rectally administered agent besides products lubricants or douching used for sexual intercourse
- 5) Continued need for, or use during the 90 days prior to enrollment, of the following medications:
 - a) Systemic immunomodulatory agents
 - b) Supraphysiologic doses of steroids
 - c) Experimental medications, vaccines, or biologicals

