During the screening visit, eligible MSM will provide written informed consent after all their questions are answered in a private exam room at the Hope Clinic. Subjects will also receive an approved HIPAA statement and will be informed about the way their protected health information will be used and stored. Copies of the consent/HIPAA form for this project will not be placed in individuals' medical records since this study collects sensitive information such as HIV status and sexual orientation.

After provision of informed consent, a medical history and physical examination will be conducted by the PI to evaluate for exclusion criteria. A rapid HIV test with finger stick whole blood (OraQuick or INSTI) will be performed by the PI or study coordinator who will be certified in HIV counseling and testing to confirm eligibility. Peripheral blood will be drawn for a complete blood count and coagulation tests. Finally, MSM will be randomized to one of three study arms:

Arm 1. Use of rectal gel lubricant alone for 7 days prior to study visit 4.

Arm 2. Use of PrEP alone for 7 days prior to study visit 4

Arm 3. Use of both rectal gel lubricant and PreP for 7 days prior to study visit 4.

TITLE OF PROJECT: PrEP, LUBE, AND THE RECTAL MUCOSA IN MSM AT RISK OF HIV
Emory IRB00077593
PRINCIPAL INVESTIGATOR: [name], MPH

This study will not be blinded, so both investigator and participant will be aware of randomization assignment. Participants will be asked to abstain from receptive anal intercourse for at least 3 days prior to study visit 2.

Visit 2:

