Study visit 2 will occur 1-6 weeks after the screening visit. During visit 2, the participant will undergo a 60mL peripheral blood draw. All blood specimens will be coded with a unique numeric identifier such that the CDC laboratories that receive the specimens will be unable to link them back to the study participants. Finally, rigid sigmoidoscopy (described further below) will be performed and, rectal secretions will be collected with Dacron swabs, and 8-12 rectal biopsies will be collected. An additional swab will be collected for testing for gonorrhea, chlamydia, and HSV-2 DNA to be performed by CDC. If positive for gonorrhea or chlamydia, men will be referred for care at their private physician's office, the health department, or AID Atlanta for treatment. HSV-2 results will not be returned to participants given the unclear clinical utility of HSV-2 serology in the absence of active disease. All men will be instructed to place nothing in the rectum and to abstain from sex for 7 days after the procedure to allow the mucosa to heal. Men will be given a follow-up appointment for visit 3 which will occur 3-16 weeks after visit 2.

Visit 3:

Study visit 3 will occur a minimum of 3 weeks (maximum 16 weeks) after study visit 2 in order to allow full healing of the rectal mucosa after biopsy and some flexibility in clinic scheduling. During visit 3, the study group assignment will be reviewed and participants will be provided applicators pre-filled with 5ml of a popular, over the counter gel lubricant and/or Truvada. Truvada will be dispensed through the Emory Investigational Drug Service. MSM assigned to study arms 1 and 3 will be instructed to insert 5mL of rectal lubricant with the study-provided pre-filled applicator once daily for 7 consecutive days prior to their scheduled study visit 4. MSM assigned to study arms 2 and 3 will be dispensed 7 days of Truvada from the Emory Investigational Drug Service and instructed on daily dosing for 7 consecutive days prior to their scheduled study visit 4. Of note, MSM in study group 3 will use rectal gel lubricant and Truvada during the same 7-day period. MSM will be requested to abstain from receptive anal intercourse while on study product (Truvada and/or lubricant).

Visit 4:

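### Open-label randomisation takes place at visit 1, at least 4 weeks before the arms first differ at visit 3, so baseline sampling and early exits happen with the arm known

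*Protocol*

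**What the plan says.** **Visit 1.** Under Procedures, Visit 1 (screening), consent is followed by history and examination: "a medical history and physical examination will be conducted by the PI to evaluate for exclusion criteria". A rapid HIV test comes next, and then: "Peripheral blood will be drawn for a complete blood count and coagulation tests. Finally, MSM will be randomized to one of three study arms". No section says that randomisation waits for the blood results. On masking, the same section says: "This study will not be blinded, so both investigator and participant will be aware of randomization assignment".

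**Laboratory exclusion.** The Exclusion Criteria list haemoglobin, PTT/INR and platelet limits under "Significant laboratory abnormalities at baseline visit for rectal biopsies, including but not limited to". The only blood count and coagulation draw described is at visit 1. Yet the Design summary attaches to visit 2 "rectal biopsy via rigid sigmoidoscopy for establishment of baseline values", and the Lay Summary has at visit 2 "rigid sigmoidoscopy for collection of baseline rectal secretions and biopsies". The criterion could refer to either visit.

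**When the arms first differ.** Visit 2 (blood, swabs, biopsies) is the same in every arm. Treatment differs only from visit 3: "During visit 3, the study group assignment will be reviewed and participants will be provided applicators pre-filled with" lubricant, and/or Truvada. The Lay Summary gives the timing: "The third study visit will occur at least 3 weeks after the second study visit (4-16 weeks after the screening visit").

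**Losses.** Study Population expects about 10-15% of men not to complete and plans 70 recruits for 60 completers; the Design summary and Project Description say 90. Study Discontinuation lets a man leave at any time. Risks of Truvada for PrEP has men discontinued when acute HIV infection is considered possible. The SAP defines no analysis population and no handling of randomised men without visit 4 data.

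**The concern.** Post-product results exist only for men who reach visit 4. In an open trial, each exit between allocation and first product is a post-randomisation loss that could in principle depend on the arm. Nothing about treatment requires the arm to be known during those weeks. The visit 2 baseline samples are also taken after an open allocation, so they are not strictly pre-randomisation measurements. Even losses unrelated to the arm leave the arms uneven by chance, and the Project Description relies on small cells: 10 men per arm for flow cytometry and 10 for the infection assay. The Protocol gives no reason for allocating at visit 1.

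**Working it through.** **1. Interval before product.** Visit 2 is 1-6 weeks after visit 1, and visit 3 is at least 3 weeks after visit 2.
- Minimum: 1 + 3 = 4 weeks, which reproduces the Lay Summary's lower limit.
- Maximum: 16 weeks in the Design summary and Lay Summary, but 6 + 16 = 22 weeks from the Visit 2 and Visit 3 sections. These need reconciling; the point does not depend on which holds.
- Visit 4 is at least 1 week after visit 3. On the shortest schedule, 4 of the 5 weeks from randomisation to visit 4 (80%) precede product.

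**2. Expected loss.**
- 70 × 0.10 = 7 and 70 × 0.15 = 10.5.
- 90 × 0.10 = 9 and 90 × 0.15 = 13.5.
- The plan's own figure: 70 × 0.85 = 59.5, so 60 completers matches the 15% end (60/70 implies 14.3% loss).

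These are expectations and not limits. The Protocol does not say whether laboratory failures are included.

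**3. What moving randomisation could gain.** Let L be total loss, assumed to fall wholly after visit 1 randomisation, and s the share of it before visit 3 (not given, so a range is shown). With randomisation at visit 3, post-randomisation loss is L(1 − s)/(1 − Ls).

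| s | L = 10% | L = 15% |
|---|---|---|
| 0 | 10% | 15% |
| 50% | 0.05/0.95 = 5.3% | 0.075/0.925 = 8.1% |
| 100% | 0% | 0% |

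**4. Arm balance when loss is independent of arm.** The method is multivariate hypergeometric. Near-equal allocation is an assumption, since the Protocol describes no allocation method.
- N = 70 as 24/23/23, 10 lost: P(20/20/20) = C(24,20) × C(23,20) × C(23,20) / C(70,60) = 0.084; P(smallest arm ≤ 18) = 0.442.
- N = 70, randomised at visit 3 after 5 of the 10 have left (65 men as 22/22/21, 5 lost): P(smallest arm ≤ 18) = 0.269. If all 10 have left, the arms are 20/20/20. If none have, nothing changes.
- N = 90 as 30/30/30, 13 lost: P(smallest arm ≤ 18) ≈ 0.00001; expected smallest arm about 24.

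**5. Precision cost of imbalance.** For 18 v 22 instead of 20 v 20: √(1/18 + 1/22) / √(2/20) = 1.005, a 0.5% larger standard error.

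**The case against.** The strongest reply is that no harm is shown. The gain in step 3 runs from nothing to everything depending on an unstated share, and the precision cost is trivial. Men must state at entry that they are willing to use the products, and staff contact them between visits to support retention; both make arm-driven withdrawal less likely. This stands, and it limits the point to a design improvement.

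A reader might infer that laboratory exclusions made with the arm known bias the comparison. The documents do not support that. The blood is drawn before allocation, so its results cannot depend on the arm, and the named limits are numerical. The list is open-ended, but nothing suggests it would be applied differently by arm. History, examination and rapid HIV test exclusions precede randomisation and are not at issue.

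A reader might also take 10-15% as a ceiling on loss, or 44% as a general risk of imbalance. The first is a planning expectation. The second holds only at 70 men and disappears at 90.

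The exit for possible acute HIV infection applies at study visits generally, including visit 4, so moving randomisation would remove only part of it. Its frequency is not given, and no position is taken on the rule itself.

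Finally, the SAP is dated 19 January 2018 and written in the past tense, so the design change may no longer be possible. That affects the remedy and leaves the observation intact.

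**Conclusion.** The point holds as a low-cost improvement. Allocation is open and precedes any arm-specific treatment by at least 4 weeks, so withdrawals, judged exits and baseline sampling in that interval all occur with the arm known. Laboratory exclusions add arm-neutral losses if results are not awaited.

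The effect on arm sizes is modest: a 44% chance of a smallest arm of 18 or fewer at 70 men (10 lost, near-equal start, loss independent of arm), and practically none at 90 (13 lost). Precision hardly changes. The size of any bias cannot be computed, because the split of losses by interval and arm is not given.

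A reader might infer that the randomised comparison is already compromised by differential dropout. The documents show the opportunity for it and no evidence that it occurs.

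**What to change.** Move randomisation from visit 1 to visit 3, after the laboratory results have been reviewed and the visit 2 samples obtained, and immediately before dispensing.

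The Project Description divides men within each arm between two assay panels and processes specimens at once, which suggests that the panel may have to be chosen at visit 2. If so, assign the panel then by a written rule and stratify the visit 3 randomisation by panel. The 10 + 10 split accounts for 20 men per arm, so the rule also has to fit whichever sample size, 70 or 90, is confirmed.

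The cost is one amendment moving a step between existing visits, with no added visits, participants or procedures. The downsides are same-day allocation and dispensing, including Truvada through the Investigational Drug Service, and a stratified list. Losses between visits 3 and 4 are unaffected, and 10 + 10 per arm is still not guaranteed.

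If enrolment is complete, leave the design as it is and report losses by arm for visits 1-2, 2-3 and 3-4.

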- 6) Intent to use HIV antiretroviral pre-exposure prophylaxis (PrEP) during the study, outside of the study procedures
- 7) Symptoms of an untreated rectal sexually transmitted infection (e.g. rectal pain, discharge, bleeding, etc.)
- 8) Current use of hormonal therapy
- 9) Any other clinical condition or prior therapy that, in the opinion of the investigator, would make the patient unsuitable for the study or unable to comply with the study requirements.

PROCEDURES

Recruitment procedures

We will recruit subjects for this protocol from 2 existing databases of MSM who have consented to be re-contacted for future research opportunities (see below). We will also recruit men with print and on-line (e.g. Facebook) advertisements as have been utilized for

other studies conducted by the Emory investigative team. We will submit all print and online advertisement copy to the Emory IRB for approval prior to launching these activities.

- 1) The Hope Clinic at Emory University maintains a large study database of research participants that have agreed to be re-contacted for future research studies. Due to the nature of ongoing studies at the Hope Clinic, a large proportion of these participants are MSM. We will utilize this study database to recruit both MSM who are engaging in URAI and men who have never engaged in anal sex. Men will be contacted by phone or email and screened by phone with the eligibility criteria for this protocol. Men who are eligible will be scheduled for a screening visit.
- 2) PRISM Health (research group in the Rollins School of Public health, [name] is a member of this group) maintains large study databases of MSM who have participated in previous research studies and have consented for future contact. Men will be contacted by phone or email and screened by phone with the eligibility criteria for this protocol. Men who are eligible will be scheduled for a screening visit.

Study visits

Visit 1 (screening):

This study will be comprised of 4 study visits over a minimum 6 week period and maximum 6 month period.

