Study visit 4 will occur a minimum of 1 week after study visit 3 and a maximum of 26 weeks from the screening visit. As above, men will be provided an appointment for study visit 4 during study visit 3. They will be instructed to use study product based on arm assignment for 7 consecutive days prior to the study visit 4 appointment. During study visit 4, the participant will undergo a 60mL peripheral blood draw. A urine sample will be collected from participants randomized to an arm containing Truvada. This sample will be used to at CDC to develop an assay to detect Truvada in the urine. All specimens will be coded with a unique numeric identifier such that the CDC laboratories that receive the specimens will be unable to link them

back to the study participants. Finally, rigid sigmoidoscopy (described further below) will be performed and, rectal secretions will be collected with Dacron swabs, and 8-12 rectal biopsies will be collected. An additional swab will be collected for testing for gonorrhea, chlamydia, and HSV-2 DNA to be performed by CDC. If positive for gonorrhea or chlamydia, men will be referred for care at their private physician's office, the health department, or AID Atlanta for treatment. HSV-2 results will not be returned to participants given the unclear clinical utility of HSV-2 serology in the absence of active disease. All men will be instructed to place nothing in the rectum and to abstain from sex for 7 days after the procedure to allow the mucosa to heal.

Contingency visit:

Attempts to ensure adherence to the study visits will be made with telephone and/or email reminders to the participant. However, if screening laboratory results are lost or are inconclusive or if a participant has been unable to adhere to study protocol, he may be rescheduled for a future date where the above visit procedures will be performed. These additional visits will be scheduled within the above visit windows.

Phone calls/retention contacts:

[figure not shown]
While on study, periodic phone calls, texts, or email reminders will occur between study staff and participants to ensure proper retention and adherence to study protocol.

Rectal biopsy procedures

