The most common risks of blood sample collection are pain at the puncture site, bruising, and a feeling of lightheadedness. To minimize these risks, blood draws will be performed by trained personnel, and will be performed in a secure environment with access to first aid equipment, bandages, and trained healthcare professionals.

Risks of Truvada for PrEP

In clinical trials of PrEP for MSM, the drug was well tolerated⁶. Nausea was more common among participants taking the medication than among those taking placebo (9% vs. 5%). There were no differences in severe or life-threatening adverse laboratory events between the active and placebo group. Adverse events associated with tenofovir can include a transient decrease in renal function and slight decreases in bone mineral density. Both of these effects occur with prolonged use of the medication and are not expected to occur with the limited 7-day dosing in this protocol.¹

Acquisition of HIV drug resistance is a theoretic concern for those taking Truvada for PrEP. However, clinical trials have shown this to be a very rare event except in those who were 'acutely' infected with HIV at the time of study enrollment. In the iPrex study, there was no drug resistant virus detected in 100 MSM who became infected after enrollment. Of the ten men who were identified retrospectively to be acutely infected with HIV at enrollment, drug resistance was detected in 2/2 of men in the active drug arm and 1/8 of men in the placebo arm⁶. For this protocol, we will test men for HIV at study entry and monitor clinically for high-risk behavior or any signs of acute HIV infection at study visits. If high risk behavior (e.g. unprotected anal intercourse with a man of unknown HIV status) or symptoms of acute HIV infection are reported, and HIV antibody test will be repeated and the participant will be counseled about the need for any follow-up testing. Clinical signs and symptoms of acute HIV infection that will be queried include: fever, fatigue, malaise, skin rash, swollen glands, oral/genital ulcers, myalgia/arthritis¹. [name] will review all reports of clinical signs/symptoms to determine appropriate follow-up and linkage to care as necessary. If a diagnosis of acute HIV infection is thought to be possible or determined by repeat HIV testing, the participant will be discontinued from the study.

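### The only HIV test scheduled in the visible text is at visit 1, yet the first Truvada dose may fall 4 to 25 weeks later; status should be rechecked at visit 3 and dosing started within 7 days

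*Protocol*

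**What the plan says.** **Testing.** The Protocol's Design paragraph places HIV testing at the first visit, among "physical examination, rapid HIV testing, phlebotomy for screening laboratories, and randomization". The Visit 1 (screening) section repeats this: "A rapid HIV test with finger stick whole blood (OraQuick or INSTI) will be performed by the PI or study coordinator". The sections for visits 2, 3 and 4 list blood draws, swabs for other infections, biopsies, dispensing and (visit 4, Truvada arms) urine. They list no HIV test. Risks of Truvada for PrEP states the overall plan: "test men for HIV at study entry and monitor clinically for high-risk behavior or any signs of acute HIV infection at study visits". It adds that an antibody test is repeated if high-risk behaviour or symptoms are reported, and that a man leaves the study if acute infection is thought possible.

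**Timing.** The Visit 3 section says: "Study visit 3 will occur a minimum of 3 weeks (maximum 16 weeks) after study visit 2". The Visit 4 section says: "Study visit 4 will occur a minimum of 1 week after study visit 3 and a maximum of 26 weeks from the screening visit". Product is dispensed at visit 3, but its use is tied to visit 4: "They will be instructed to use study product based on arm assignment for 7 consecutive days prior to the study visit 4 appointment". The Study visits section also gives an overall span: "This study will be comprised of 4 study visits over a minimum 6 week period and maximum 6 month period".

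**Abstinence.** Inclusion criterion 8 reads: "Willing to abstain from receptive anal intercourse 3 days prior to study visit 2 and 10 days prior to study visit 4". Criterion 9 adds one week after each of those visits.

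The SAP does not touch on HIV testing.

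**The concern.** The Protocol names its own hazard. In Risks of Truvada for PrEP it calls drug resistance very rare except in men acutely infected when they enrolled. From the cited PrEP efficacy trial it reports resistance in 2 of 2 such men on active drug and 1 of 8 on placebo, against none in 100 men infected after enrolment. If enrolment there is read as the start of drug, which the Protocol does not spell out, what matters is HIV status when dosing begins. This trial schedules its check at screening, which the windows separate from the first dose by at least 4 weeks.

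Two kinds of participant could then start Truvada with undiagnosed HIV: a man infected after screening in whom nothing is reported or noticed at visits 2 and 3, and a man infected between visit 3 and the first dose. Exposure is plausible, because eligible men report receptive anal sex in the last 6 months.

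**Working it through.** **Inputs (Protocol).**
- Visit 2: 1 to 6 weeks after screening (Visit 2).
- Visit 3: 3 to 16 weeks after visit 2 (Visit 3); the Design paragraph gives 4 to 16 weeks from screening.
- Visit 4: at least 1 week after visit 3 and at most 26 weeks from screening (Visit 4).
- Dosing: the 7 days before visit 4 (Visits 3 and 4).
- Minimum study period: 6 weeks (Study visits).
- Abstinence: 3 days before visit 2, 7 days after it, 10 days before visit 4 (Inclusion criteria 8 and 9).

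**1. Reproduce the plan's own figure.** Earliest visit 4 = 1 + 3 + 1 = 5 weeks. The Lay Summary gives 5 to 26 weeks, so the lower end is reproduced; 26 is the stated cap.

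**2. Visit 1 test to first dose.** First dose = visit 4 minus 1 week.
- Earliest: 5 − 1 = 4 weeks (28 days).
- Earliest under the 6-week minimum: 6 − 1 = 5 weeks (35 days).
- Latest: 26 − 1 = 25 weeks (175 days).

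Had dosing begun on the day of visit 3, the range would be 4 to 16 weeks (Design) or 4 to 22 weeks (6 + 16 = 22, Visit 2 and Visit 3 sections). The text ties dosing to visit 4, so 4 to 25 is the right reading.

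**3. Visit 3 to first dose.** The shortest gap is 0. The longest depends on when visit 3 falls:

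| Visit 3 at week | Longest gap to first dose |
|---|---|
| 4 | 25 − 4 = 21 weeks (147 days) |
| 16 | 25 − 16 = 9 weeks |
| 22 | 25 − 22 = 3 weeks |

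No visit is scheduled in this gap, and only the week 26 limit on visit 4 bounds it.

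**4. Abstinence requested between test and first dose.** 3 + 7 + (10 − 7) = 13 days. Days with no such request:
- shortest schedule: 28 − 13 = 15;
- shortest under the 6-week minimum: 35 − 13 = 22;
- longest schedule: 175 − 13 = 162.

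These count days without an abstinence request, not days without any protection.

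**5. With a visit 3 retest and a 7-day cap.**
- Latest scheduled test to first dose: 0 to 7 days, of which at most 7 − 3 = 4 carry no abstinence request.
- Visit 3 to visit 4: 7 to 14 days.
- Latest visit 4: week 16 + 2 = 18 (Design window) or 6 + 16 + 2 = 24 (Visit 3 section).
- The 6-week minimum stays feasible: visit 3 at week 4, visit 4 at week 4 + 2 = 6.

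**6. Recent infection missed by an antibody test.** Let the test miss infections from the previous *w* weeks; the documents give no value. The period in which an infection escapes the latest scheduled test is 4 + *w* to 25 + *w* weeks now, and *w* to 1 + *w* with the change. Purely as an assumption, *w* of 2 to 4 gives 6 to 29 weeks now and 2 to 5 with the change. For a given schedule, moving the latest test from visit 1 to visit 3 shortens the period by the time between those visits, at least 4 weeks whatever *w* is.

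**The case against.** **The schedule may not be fully visible.** Figure 1, the visit summary, is not reproduced, and the HIV risk counseling section mentions testing without naming a visit. A reader might infer that the plan certainly has no retest; the documents do not allow that. Still, the undated sentence schedules nothing, and Risks of Truvada for PrEP explicitly describes a test at entry followed by clinical monitoring. The point is therefore confined to the visible text.

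**Safeguards exist.** A reader might infer that nothing but a man's own report could reveal an infection after visit 1. That is too strong:
- Signs are monitored at visits, and some of those listed, such as rash or swollen glands, can be observed.
- Discontinuation needs only that acute infection be thought possible.
- A contingency visit can repeat visit procedures if results are lost or inconclusive, or after non-adherence.
- Adverse events may be reported between visits (AE Reporting).
- Free condoms and risk-reduction counselling go to all men.

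All of this stands. None of it confirms HIV status close to dosing in a man who appears well and reports nothing. The phone and text contacts are described as serving retention and adherence, not this query.

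**The long gaps are extremes.** This is true. The 25-week interval needs the latest visit 4, and the 21-week gap also needs the earliest visit 3. Nothing suggests either is typical. The shortest permitted interval, however, is already 4 weeks.

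**The remedy fits the evidence imperfectly.** An antibody retest is weakest for very recent infection, which is the group in the cited resistance data. That group is two men on active drug, whose time on drug is not given, while dosing here lasts 7 days. This stands, and it is why the query must accompany the test. The retest adds value for infections acquired earlier in the weeks since screening.

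**The lubricant-only arm has no resistance risk.** This is correct. Testing there serves comparability between arms, not safety from Truvada.

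**Conclusion.** The concern holds for the visible text. The only scheduled HIV test precedes the first Truvada dose by 4 to 25 weeks (5 to 25 under the 6-week minimum), and the interval from visit 3 to first dose is limited only by week 26 for visit 4. The plan thus does not confirm HIV status at the start of dosing, which is where its own resistance rationale applies.

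This is a gap in a safety check, not a demonstrated harm. A reader might go on to infer that some number of men will start Truvada infected, or that resistance will follow. The documents support neither: they give no HIV incidence, no resistance data for a 7-day course, and no expected distribution of visit dates.

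The conclusion assumes that dosing follows the text (the week before visit 4) and that Figure 1 schedules no retest at or after visit 3 and before dosing. The change is worth making because it is cheap and bears on participant safety. Confidence is moderate, mainly because Figure 1 cannot be seen.

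**What to change.** 1. **Retest at visit 3, before dispensing.** Repeat the rapid finger-stick test and record the risk and symptom query from Risks of Truvada for PrEP. Safety requires this in the two Truvada arms. All three arms are preferable, so that detection and removal do not differ by arm. Dispense only if the test is negative and the query raises no concern; otherwise follow the existing steps in that section.
2. **Cap the delay.** Start product within 7 days of visit 3, so that visit 4 falls 7 to 14 days after visit 3. If that slips, repeat the test and the query before the first dose.

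If Figure 1 already schedules a retest at or after visit 3 and before dosing, only the cap is needed.

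**Cost.** A protocol amendment and one extra finger-stick per man reaching visit 3 (at most 70 or 90, the enrolment totals in Study Population and Design), by existing staff at an existing visit. The visit 4 appointment is already made at visit 3, so the cap needs no new procedure, but scheduling becomes less flexible: the permitted visit 3 to visit 4 interval shrinks from 1 to 22 weeks (26 − 4 = 22) to 1 to 2 weeks. A late visit 4 may mean an extra attendance. Some risk remains, because an antibody test can miss very recent infection and up to 7 days may pass before dosing.
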